3.1.2 Treatment regimens

For objective 1, groups of patients using the following treatment regimens are analysed:

1. Short-acting bronchodilators as required only (SABA and/or SAMA)
2. Maintenance therapy with LAMA and/or LABA
3. ICS / LABA in combination inhaler
4. Triple therapy: ICS + LABA + LAMA

Treatment category will be assessed based on ≥ 1 prescriptions in the baseline year.

3.1.3 Medication Possession Ratio

MPR (the proportion of days covered by prescriptions) will be calculated by dividing the total of one day's supply by the total number of days evaluated, multiplied by 100%. The evaluation period for every person is 365 days in the baseline year.

3.2 Outcomes

3.2.1 COPD exacerbations

The primary outcome for sub-study 1 will be the number of COPD exacerbations in the outcome period, defined as the occurrence of one or more of the following events:

- a. Respiratory-related hospital attendance / admission AND/OR
- b. Respiratory-related A&E attendance AND/OR
- c. An acute oral corticosteroid course AND/OR
- d. Antibiotics prescribed with evidence of a lower respiratory consultation

Where ≥ 1 of these events occur within 2 weeks of each other, they will be considered to be the result of the same exacerbation (and will only be counted once).

The number of acute oral corticosteroids courses will be analysed as secondary outcome for sub-study 1.

A sensitivity analysis will be performed with a more specific (but less sensitive definition) of acute oral corticosteroids courses with evidence of a lower respiratory consultation (Read code for lower respiratory consultation with prescription).

3.2.2 Hospital admissions in HES linked data

1. Hospital admissions as the index date for objective 2:
Occurrence of a hospital admission (spell) for COPD exacerbation in HES linked data: ≥ 1 of the following ICD-10-CM codes in any diagnostic position (Appendix 6.1):
 - a. J44.0: Chronic obstructive pulmonary disease with acute lower respiratory infection
 - b. J44.1: Chronic obstructive pulmonary disease with (acute) exacerbation
2. Hospital re-admission as outcome event:
Occurrence of a hospital admission (spell) for COPD in HES linked data:
 - a. ICD-10 codes J44.0 or J44.1: COPD exacerbations in any diagnostic position
 - b. ICD-10 codes J40-J44: any COPD-related code as primary diagnosis

3.2.3 Mortality

1. All-cause mortality will be assessed by the combined information on:
 - a. Death in hospital, based on HES data
 - b. Death outside hospital, based on GP records

3.2.4 Health care Resource Use

The following outcomes of HRU are described in the baseline year and outcome year in patients with HES data available.⁴

1. Physician office visits:
 - a. Total number of General Practice (GP) surgery consultations
 - b. Number of COPD-related GP consultations
2. Outpatient visits:
 - a. Total number of referrals to specialist
 - b. Number of referrals to specialist for COPD or other lower respiratory conditions
3. Accident & Emergency (A&E) attendances / out of hours services:
 - a. Total number of A&E attendances
 - b. Total number of GP out-of-hours consultations
 - c. Number of A&E attendances for COPD or other lower respiratory conditions
4. Hospital admissions: Number of hospital admissions (spells):
 - a. For all-causes
 - b. With COPD exacerbations (ICD-10 J44.0 or J44.1) as primary diagnosis
 - c. With COPD exacerbations ICD-10 J44.0 or J44.1 as secondary / subsidiary diagnosis and respiratory conditions (ICD-10 J00-J99) as primary diagnosis
5. Number of COPD-related drug prescriptions:
 - a. Fixed dose combination (FDC) of inhaled corticosteroids (ICS) and Long-acting β 2-agonists (LABA)
 - b. Stand-alone ICS
 - c. Stand-alone LABA
 - d. Stand-alone LAMA
 - e. FDC LAMA / LABA
 - f. Short-acting β 2-agonists (SABA)
 - g. Short-acting Muscarinic Antagonists (SAMA)
 - h. Theophylline
 - i. Oral corticosteroids
 - j. Antibiotics prescribed with lower respiratory consultation Read code
6. Total number of drug prescriptions for all causes

Outcomes are described as mean numbers (\pm standard deviation (SD)) and as categorical variables (0, 1, 2, 3, ≥ 4 for outpatient visits, A&E attendances and hospitalisations; 0, 1-4, 5-8, 9-12, 13-24, ≥ 25 for GP consultation; ≥ 1 prescription (yes/no) for drugs)

⁴ Events occurring at index date are counted in the baseline year, except medication prescriptions which are counted in the outcome year

3.2.5 Costs of Health care Resource Use

Cost data for primary consultation services provided are obtained from the most recent publication of the 'Unit Costs of Health & Social Care', prepared by the Personal Social Services Research Unit (PSSRU) at the time of analyses.

Costs for COPD or respiratory related services provided in secondary care are obtained from 'NHS Reference cost schedule 2014 to 2015', prepared by the Department of Health⁵ or a more recent version when available.

Prices assigned to drugs are taken from the NHS dictionary of medicines and devices (DM+D) browser (<http://dmd.medicines.org.uk/>). DM+D provides up to date costs for Systematized Nomenclature of Medicine Clinical Terms (SnoMed) codes. Read codes are mapped to SnoMed codes and costs are calculated for the following medications:

1. Inhaled Corticosteroids (ICS)
2. Long-Acting β -2 Agonists (LABA)
3. Short-Acting β -2 Agonists (SABA)
4. Short-Acting Muscarinic Antagonists (SAMA)
5. Long-Acting Muscarinic Antagonists (LAMA)
6. Oral corticosteroids (maintenance and rescue courses)
7. Theophyllines
8. Antibiotics prescribed for lower respiratory events

Total all-cause and COPD-related costs are calculated as the sum of costs related to the respective HRU outcomes mentioned above.

⁵ <https://www.gov.uk/government/publications/nhs-reference-costs-2014-to-2015>

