1.4 Objectives

1. To study the association between high blood eosinophil counts at the time of stable COPD (i.e., no recent exacerbation and stable treatment during the study period) and the prospective exacerbation rate in different subgroups of patients with COPD defined by treatment regimen and smoking habits and to study whether this association is also found in patients with good adherence to ICS
2. To study whether patients admitted to hospital for COPD exacerbation are more likely to be re-admitted if their pre-admission eosinophil count (assessed at the time when there was no recent exacerbation) is high
3. A. To estimate mean all-cause and COPD-related health care resource use (HRU) and associated costs in 4 subgroups of patients who are at risk of exacerbations (i.e. a history of ≥ 2 exacerbations or ≥ 1 exacerbation leading to hospitalisation in the past 12 months) while receiving treatment with triple therapy, where the 4 subgroups are defined by the presence or absence of high blood eosinophil counts and current smoking habits
B. to compare HRU and costs with those for the total population of patients with COPD who have blood eosinophil counts available
4. To study whether the presence of high blood eosinophil counts is associated with greater all-cause and COPD-related costs in the subsequent year and to study which other easily accessible characteristics drive future costs in patients with COPD

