2. METHODOLOGY

2.1 Study Design – General Aspects

2.1.1 Data Sources

Dataset of patients from Clinical Practice Research Datalink (CPRD) and the Optimum Patient Care Research Database (OPCRD) will be used for analyses.

CPRD¹, formerly known as the General Practice Research Database (GPRD), is a computerised longitudinal research database containing anonymised medical record data from approximately 650 subscribing UK primary care practices.

OPCRD² is a respiratory-enriched primary care research database compiled by Optimum Patient Care providing chronic respiratory review services. It contains anonymous, longitudinal data extracted from over 550 UK practices (>178.000 patients with COPD). It is approved by Trent Multi Centre Research Ethics Committee for clinical research use and offers a high-quality data source that is used regularly in clinical, epidemiological and pharmaceutical research.

Both datasets are constructed separately using data in a patient unidentifiable manner

Sub-study 1 will use patient data extracted from the Optimum Patient Care Research Database (OPCRD). The OPCRd is developed, maintained, and owned by Optimum Patient Care (OPC), a social enterprise company that aims to improve patient outcomes through medical research and services. OPC provides evidence-based recommendations to UK general practices through bespoke software and practice reports.

For sub-studies 2, 3 and 4, data of patients from the Clinical Practice Research Datalink (CPRD) with linkage to HES Admitted Patient Care and HES A&E and outpatient datasets will be used. CPRD data will be extracted through AZ's account.

¹ <https://www.cprd.com>

² See <http://optimumpatientcare.org/opcrd/>

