The risk of COPD-related re-admission to hospital for COPD within 4 weeks and 1 year will be compared for patients with and without high blood eosinophil counts year prior to index date. All analyses will be adjusted for potential confounders in multiple regression analysis.

[figure not shown]

Figure 3. Study design objective 2

2.5.3 Objective 3

The ID of objective 3 will be the most recent blood eosinophil count recorded at the time of no recent exacerbation (Figure 4).

HRU and costs, broken down by type of utilisation and total costs will be assessed in both a baseline year prior to ID and a follow-up year (outcome year) after ID.

Mean all-cause and COPD-related HRU and associated costs will be estimated in one follow-up year after the eosinophil count in the following 4 subpopulations, defined in a baseline year, of patients with COPD on triple therapy, who are at high risk of exacerbations (i.e. a history of ≥ 2 exacerbations or ≥ 1 exacerbation leading to hospitalisation in the baseline year):

Patients with high blood eosinophil counts who are:

1. not actively smoking
2. actively smoking

Patients with normal blood eosinophil counts who are:

3. not actively smoking
4. actively smoking

Mean HRU and costs will be compared with values observed in the total population of patients with COPD who have blood eosinophil counts available.

Figure 4. Study design 2

[figure not shown]

Figure 4. Study design objective 3

2.5.4 Objective 4

The ID of objective 4 will be the most recent blood eosinophil count recorded at the time of no recent exacerbation with one baseline year prior to index date for assessment of potential predictors of costs.

Total all-cause and COPD-related medical costs will be assessed in the outcome year after ID (Figure 5).

Two multiple regression analyses will be performed with total all-cause costs and total COPD-related costs as outcome variables. All potential predictors will be evaluated as independent variables, including blood eosinophil counts and its interaction with smoking status.

[figure not shown]

Figure 5. Study design objective 4

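### Protocol 3.2.5 defines an all-cause cost total that its own price rules do not cover: drug costing is limited to eight respiratory-use classes, and the secondary-care source is stated for respiratory services only

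*Protocol*

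**What the plan says.** Objective 3 in Protocol 1.4 is "To estimate mean all-cause and COPD-related health care resource use (HRU) and associated costs in 4 subgroups of patients" at risk of exacerbation on triple therapy. For objective 4, Protocol 2.5.4 states "Two multiple regression analyses will be performed with total all-cause costs and total COPD-related costs as outcome variables".

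Protocol 3.2.4 counts resource use in pairs. The all-cause side covers every GP consultation (1a), every specialist referral (2a), every A&E attendance (3a), GP out-of-hours contacts (3b), admissions for any cause (4a) and item 6, "Total number of drug prescriptions for all causes".

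Protocol 3.2.5 then sets the prices:
- Primary care consultations use the PSSRU unit costs, with no disease restriction.
- Secondary care: "Costs for COPD or respiratory related services provided in secondary care are obtained from" the NHS reference cost schedule.
- Drugs use DM+D prices: "Read codes are mapped to SnoMed codes and costs are calculated for the following medications". The list that follows has eight entries: ICS, LABA, SABA, SAMA, LAMA, oral corticosteroids, theophyllines, and antibiotics for lower respiratory events.
- Totals: "Total all-cause and COPD-related costs are calculated as the sum of costs related to the respective HRU outcomes mentioned above".

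On outpatient care, Protocol 2.1.1 says that for sub-studies 2 to 4 CPRD data "with linkage to HES Admitted Patient Care and HES A&E and outpatient datasets will be used". The outpatient item in 3.2.4 is nevertheless "Total number of referrals to specialist", with a respiratory counterpart.

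**The concern.** The last sentence of 3.2.5 promises a total over all-cause items, while the sentences before it supply prices for only part of them. An analyst who follows the drug list literally has no price for a statin, insulin or an antidepressant. One who follows the secondary-care sentence literally has no price for a cardiac admission. Another analyst, working from the definition of the total, would price everything. The two would report different quantities under the same name.

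This bears on the mean costs and cost ratios of sub-study 3 and on one of the two regressions of sub-study 4. Sub-study 4 also asks which characteristics drive cost. The candidate predictors in 3.3.3 include diabetes, ischaemic heart disease, heart failure, chronic kidney disease and psychiatric conditions. Part of what they cost would be expected to lie in the items without a stated price, so the AIC selection could change.

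**Working it through.** **Step 1: set the all-cause items of 3.2.4 against the prices in 3.2.5.**

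| All-cause item in 3.2.4 | Price stated in 3.2.5 | Covered as written? |
|---|---|---|
| 1a GP consultations | PSSRU | Yes, any cause |
| 3b GP out-of-hours | PSSRU, read as primary care | Yes, any cause |
| 2a specialist referrals | Reference costs, respiratory services | Respiratory part only |
| 3a A&E attendances | Reference costs, respiratory services | Respiratory part only |
| 4a admissions | Reference costs, respiratory services | Respiratory part only |
| 6 all prescriptions | DM+D, eight classes | Eight classes only |

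The drug row is the firm one, because the text says which medications are costed. The three secondary-care rows depend on whether the respiratory wording is a limit or loose drafting.

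**Step 2: does the all-cause total collapse into the COPD-related one?** No. Even on the narrowest reading it adds GP consultations not related to COPD (1a beyond 1b) and out-of-hours contacts (3b). It also adds respiratory admissions without a J44.0 or J44.1 code, which 4b and 4c leave out of the COPD-related items.

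**Step 3: effect on level and ratio.** In the reference group (normal eosinophils in sub-study 4, the total population in sub-study 3), let s be the share of true all-cause cost left unpriced. Let Rp be the cost ratio for priced items and Ru the ratio for unpriced items. Then:
- mean as written = (1 − s) × true mean in the reference group, a shortfall of s;
- true ratio = (1 − s) × Rp + s × Ru;
- ratio as written = Rp;
- error = Rp − true ratio = s × (Rp − Ru).

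The protocol gives none of s, Rp or Ru, so the values below are assumptions chosen to show the range. A share of 0.2 stands for a small gap, such as drugs alone; the larger shares stand for drugs plus hospital care.

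| s | Rp 1.30, Ru 1.00: true ratio (error) | Rp 1.30, Ru 1.30: true ratio (error) | Rp 1.00, Ru 1.30: true ratio (error) |
|---|---|---|---|
| 0.2 | 1.24 (+0.06) | 1.30 (0) | 1.06 (−0.06) |
| 0.4 | 1.18 (+0.12) | 1.30 (0) | 1.12 (−0.12) |
| 0.6 | 1.12 (+0.18) | 1.30 (0) | 1.18 (−0.18) |
| 0.7 | 1.09 (+0.21) | 1.30 (0) | 1.21 (−0.21) |

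For example, at s = 0.4 in the first column: 0.6 × 1.30 + 0.4 × 1.00 = 1.18. The level is too low in every row. The ratio can be too high, right or too low.

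**Step 4: sample sizes.** Those in 3.6.3 and 3.6.4 are not at issue. With 10% high counts, two-sided α = 0.05 and 80% power, the normal approximation gives 873 + 97 = 970 for 0.3 SD (979 stated) and 1,963 + 219 = 2,182 for 0.2 SD (2,200 stated). They are in SD units, so no price enters them.

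**Step 5: outpatient measure.** Item 2 is headed as visits and tabulated as visits, but counts referrals. A referral can lead to no attendance or to several. The linked HES outpatient data would allow attendances to be counted.

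**The case against.** The strongest reply is that 3.2.5 never says that other care is excluded. Its closing sentence defines the total over all-cause items, and the synopsis bases costs on NHS reference costs without a respiratory limit. On that reading, the secondary-care sentence is loose and a unit-cost source is merely unstated, which a SAP or costing manual could supply. For hospital care this has force, so omission there is possible but not established. It does not rescue the drug list, which is a stated rule in conflict with item 6 and with the definition of the total.

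A reader might infer three stronger things, and the protocol supports none of them:
- That one sub-study 4 outcome duplicates the other. All GP and out-of-hours contacts are priced, so the two differ.
- That the cost ratio is inflated by a known amount. The only ratios of 1.3 used for planning in the protocol concern exacerbation rates and re-admission hazards, not costs, and the direction of the error depends on an unknown contrast.
- That counting referrals makes the total not all-cause. Item 2a counts every referral, so this is a separate measurement problem.

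**Conclusion.** The point holds as an internal contradiction in 3.2.5. Costed as written, the all-cause total leaves out non-respiratory drug costs. If the secondary-care wording is meant literally, it also leaves out non-respiratory admissions, A&E and outpatient costs. The mean is then too low by the unpriced share, which the protocol does not allow anyone to estimate. The consequence for the cost ratios and for predictor selection is unknown in size and direction. The all-cause outcome would sit closer to the COPD-related one than objectives 3 and 4 intend. The outpatient measure is a lesser, separate weakness affecting both totals. The conclusion rests on the protocol alone; a SAP that prices all items would have to override the drug list in 3.2.5.

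**What to change.** In Protocol 3.2.5:
- Apply DM+D prices to all prescriptions for all-cause cost, and keep the eight classes for COPD-related cost only.
- Apply the NHS reference cost schedule to all HES admissions, A&E attendances and outpatient attendances, respiratory or not.
- If this cannot be done, rename the outcome in objectives 3 and 4 and in 3.4.3 and 3.4.4 so that it matches what is priced.

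Separately, in Protocol 3.2.4 item 2, count attendances from the linked HES outpatient data (all, and respiratory) instead of referrals.

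The cost is a change of wording and extra price mapping, chiefly for non-respiratory drugs and admissions. The HES linkage is already planned in 2.1.1 and all prescriptions are already counted in 3.2.4, so no new data source is needed. The change should be made before any costs are calculated.

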3.3 Other Variables and Covariates

3.3.1 Patient demographics / baseline characterisation

The following baseline characteristics will be described for comparison groups:

1. Age group at index date (years):
2. Sex
3. Smoking status, Read code closest to and within 5 years prior to index date
 - a. Never smoker
 - b. Ex-smoker
 - c. Current smoker
4. BMI, calculated from height and weight data if available⁶ and taken from practice recorded BMI value if not, within 10 years prior to index date
 - a. Underweight: <18.5
 - b. Normal weight: ≥ 18.5 and <25
 - c. Overweight: ≥ 25 and <30
 - d. Obese: ≥ 30
5. Comorbidities (Diagnostic Read code prior to index date):
 - a. Asthma
 - a. Never
 - b. Active⁷
 - c. Ever, not active
 - b. Allergic / non-allergic rhinitis
 - a. Never
 - b. Active
 - c. Ever, not active
 - c. Eczema diagnosis
 - a. Never
 - b. Active
 - c. Ever, not active
 - d. Nasal polyps ever
 - e. Helminth infections
 - f. Chronic sinusitis diagnosis ever
 - g. Gastro-oesophageal reflux disease (GERD)
 - h. Diabetes Mellitus ever
 - i. Osteopenia / Osteoporosis ever
 - j. Hypertension ever
 - k. Obstructive Sleep apnoea ever
 - l. Cataract ever
 - m. Ischaemic heart disease ever
 - n. Heart failure ever

⁶ Weight (kg) divided by height (metres) squared

⁷ For comorbidities, 'active' refers to those for which a diagnosis was recorded within the baseline year and/or a prior diagnosis was accompanied by a prescription for the comorbidity within the baseline year. 'Ever' refers to diagnosis at any time before or during the baseline period

- o. Psychiatric conditions / Anxiety/ Depression ever
 - p. Sleep disorders ever
 - q. Chronic kidney disease ever
 - r. Osteoporosis (Read code diagnosis or osteoporosis drugs [bisphosphonates, denosumab, strontium ranelate or teriparatide] ever
6. Charlson co-morbidity index: based on diagnoses ever
- a. 0
 - b. 1-4
 - c. 5-9
 - d. ≥ 10
7. Most recent FEV₁ % predicted, mean (SD) and categorical
- a. $\geq 80\%$
 - b. 50–79%
 - c. 30-49%
 - d. $< 30\%$
 - e. Unknown
8. Modified Medical Research Council (MRC) dyspnoea score, within 5 years of the index date
- a. 0-1
 - b. ≥ 2
 - c. Unknown
9. GOLD groups, defined based on a combined assessment of symptoms, spirometry and exacerbation risk as follows:
- a. GOLD A: FEV₁ % predicted ≥ 50 and ≤ 1 COPD exacerbation and no hospitalization for COPD in baseline year and mMRC 0–1
 - b. GOLD B: FEV₁ % predicted ≥ 50 and ≤ 1 COPD exacerbation and no hospitalization for COPD in baseline year and mMRC ≥ 2
 - c. GOLD C: FEV₁ % predicted < 50 or ≥ 2 COPD exacerbations or ≥ 1 hospitalization for COPD in baseline year) and mMRC 0–1
 - d. GOLD D: FEV₁ % predicted < 50 or ≥ 2 COPD exacerbations or ≥ 1 hospitalization for COPD in baseline year) and mMRC ≥ 2
 - e. Unknown
10. ICS/LABA combinations prescribed with dosages (most recent in the baseline year)
- a. Budesonide / formeterol (Symbicort[®] / DuoResp Spiromax[®])
 - b. Fluticasone propionate / salmeterol (Seretide[®])
 - c. Beclomethasone / formeterol (Fostair[®])
 - d. Fluticasone furoate / vilanterol (Relvar Ellipta[®])
11. Cumulative doses prescribed in the baseline year (expressed as average dose per day):
- a. Average cumulative ICS dose
 - b. Average cumulative SABA dose
 - c. Average cumulative SAMA dose

